### **5.3 Safety Analysis Set (SAF)**

The SAF is defined as all subjects who received at least one dose of the study drug.

### **5.4 Pharmacokinetic Analysis Set (PKAS)**

The PKAS will consist of all subjects who receive at least one dose of the study drug and who provide samples for drug concentrations for at least one time point.

### **5.5 Pharmacodynamic Analysis Set (PDAS)**

All subjects who receive at least one dose of the study drug and who provide samples for the determination of pharmacodynamic parameters at least one time point will be included in the PDAS.

## **6 ANALYSIS VARIABLES**

### **6.1 Efficacy Endpoints**

#### **6.1.1 Primary Efficacy Endpoints**

There are two primary efficacy endpoints.

- ACR20 response rate at Week 12 or early termination (Week 12/ET)

- Change from baseline in mTSS at Week 28 or early termination (Week 28/ET) (suppression of joint destruction)

### **Definitions**

#### **ACR20 response rate at Week 12 or early termination (Week 12/ET)**

It is defined as percentage of subjects achieving ACR 20 response at Week 12/ET, based on C-reactive protein (CRP). ACR20 is a binary variable, with levels responder and non-responder.

#### **Responder :**

A subject will be defined as an ACR20-CRP responder at any time point (e.g. Week 12/ET) if the subject meet ALL the following American College of Rheumatology (ACR) response criteria:

- At least 20% reduction from baseline at the time point (e.g. Week 12/ET) in the number of 68 tender joint count (TJC-68)

AND

- At least 20% reduction from baseline at the time point (e.g. Week 12/ET) in the number of 66 swollen joint count (SJC-66)

AND

- At least 20% reduction from baseline at the time point (e.g. Week 12/ET) in ANY 3 or more of the 5 following ACR components
  - Subject's global assessment of arthritis pain (SGAP) (assessed using a 100 mm VAS ; score of 0 indicates no pain, and score of 100 indicates very severe pain)
  - Subject's global assessment of arthritis (SGA) (assessed using a 100 mm VAS; score of 0 indicates no disease activity, and score of 100 mm indicates very severe disease activity)
  - Physician's global assessment of arthritis (PGA) ((assessed using a 100 mm VAS; score of 0 indicates no disease activity, and score of 100 mm indicates very severe disease activity)
  - Health Assessment Questionnaire – Disease Index (HAQ-DI; score ranges from 0 to 3 with higher scores indicating greater disability)
  - CRP (Higher values indicate greater inflammation)

Baseline is defined in Section 7.11.3. A negative percent change indicates a reduction from baseline (i.e., a favorable outcome).

If the baseline value is 0 in some of ACR components, then that component is regarded as non-responder at that component and used for ACR calculation. The handling of missing data in ACR components is described at Section 7.11.1.

Non-responder: A subject will be defined as an ACR20-CRP non-responder at the time point (e.g. Week 12/ET), if the subject does not meet the ACR20-CRP responder criteria.

### **Change from baseline in mTSS at Week 28 or early termination (Week 28/ET) (suppression of joint destruction)**

The severity of joint destruction in hands and feet (bone erosion and joint fissure narrowing) will be assessed by the third party through the mTSS method by scoring the severity of bone erosion and joint fissure narrowing of the target joints and calculate the total score. The target joints and the scoring method are described in the SOP prepared by the third party institution.

The results of the assessment will be sent to the sponsor by the third party institution.

The higher scores in mTSS represent greater damage and the positive change from baseline in mTSS represents unfavorable values.

## **6.1.2 Secondary Efficacy Variables**

### **6.1.2.1 Categorical Variables**

- Percentage of subjects achieving ACR 20/50/70-CRP response at each analysis visit (except ACR20 Week 12/ET)
- Percentage of subjects achieving ACR 20/50/70-ESR response at Week 12/ET

Note: ACR 20-ESR response is similar to definition in 6.1.1 by replacing CRP with ESR.

- Percentage of subjects achieving ACR20-CRP response at Week 4 and sustaining the response at Weeks 8 and 12
- Percentage of subjects achieving ACR20-CRP response at Week 8 and sustaining the response at Week 12
- Percentage of subjects achieving mTSS change from baseline  $\leq 0.5$  at each analysis visit
- Percentage of subjects achieving mTSS change from baseline  $\leq 0$  at each analysis visit
- Percentage of subjects showing Clinically Relevant Radiographic Progression: CRRP (mTSS change from baseline  $\geq 3$ ) at each analysis visit
- Percentage of subjects showing Rapid Radiographic Progression: RRP (Yearly progression of mTSS  $\geq 5$ )

#### Calculation DAS-CRP/ESR response:

DAS-CRP/ESR response is consist of following parameters, and calculated according to below description.

- TJC (28 joints)
- SJC (28 joints)

- CRP or ESR
- SGA

[When CRP is used]  

$$\text{DAS28} = 0.56\sqrt{(\text{TJC})} + 0.28\sqrt{(\text{SJC})} + 0.36 \ln (\text{CRP} + 1) + 0.014 \times \text{SGA} + 0.96$$

[When ESR is used]  

$$\text{DAS28} = 0.56\sqrt{(\text{TJC})} + 0.28\sqrt{(\text{SJC})} + 0.70 \ln \text{ESR} + 0.014 \times \text{SGA}$$

Note: CRP values measured in mg/dL will be converted to mg/L for analysis purposes as: value in mg/L = value in mg/dL × 10; SGA is measured on 100 mm VAS. If any component is a missing value, then DAS28-CRP/ESR will be a missing value. If ESR is 0 then DAS28-ESR is missing.

- Percentage of subjects achieving DAS28-CRP score <2.6 at each analysis visit
- Percentage of subjects achieving DAS28-ESR score <2.6 at each analysis visit
- Percentage of subjects achieving DAS28-CRP score ≤3.2 at each analysis visit
- Percentage of subjects achieving DAS28-ESR score ≤3.2 at each analysis visit

Definition EULAR:

DAS28 after treatment	DAS28 improvement (DAS28 before treatment - DAS28 after treatment)		
	> 1.2	> 0.6 and ≤ 1.2	≤ 0.6
≤ 3.2	Good response	Moderate response	No response
> 3.2 and ≤ 5.1	Moderate response	Moderate response	No response
> 5.1	Moderate response	No response	No response

- Percentage of subjects in DAS28-CRP EULAR response criterion of "Good Response" at each analysis visit
- Percentage of subjects in DAS28-ESR EULAR response criterion of "Good Response" at each analysis visit
- Percentage of subjects in DAS28-CRP EULAR response criterion of "Good Response" or "Moderate Response" at each analysis visit
- Percentage of subjects in DAS28-ESR EULAR response criterion of "Good Response" or "Moderate Response" at each analysis visit
- Percentage of subjects achieving ACR/EULAR score for remission at each analysis visit  
 If all of the following 4 parameters are fulfilled, it is defined as remission:
  - TJC (68 joints) ≤ 1
  - SJC (66 joints) ≤ 1
  - CRP ≤ 1 mg/dL
  - SGA ≤ 1 cm (on a VAS of 0-100 mm).

Note: All 4 conditions must be fulfilled to be in remission. If any component is a missing value, then ACR/EULAR score for remission will be a missing value.

- Percentage of subjects with a SDAI score of  $\leq 3.3$  at each analysis visit  
SDAI score is consist of following parameters, and calculated according to below description.
  - TJC (28 joints)
  - SJC (28 joints)
  - SGA (0-10 cm VAS)
  - PGA (0-10 cm VAS)
  - CRP (mg/dL)

$$\text{SDAI} = \text{TJC} + \text{SJC} + \text{SGA} + \text{PGA} + \text{CRP}$$

Note: If any component is a missing value, then SDAI score will be a missing value.

- Percentage of subjects with a CDAI score of  $\leq 2.8$  at each analysis visit  
CDAI score is consist of following parameters, and calculated according to below description.
  - TJC (28 joints)
  - SJC (28 joints)
  - SGA (0-10 cm VAS)
  - PGA (0-10 cm VAS)

$$\text{CDAI} = \text{TJC} + \text{SJC} + \text{SGA} + \text{PGA}$$

Note: If any component is a missing value, then CDAI score will be a missing value.

- Percentage of subjects achieving HAQ-DI ( $\leq 0.5$ ) at each analysis visit
- Percentage of subjects achieving decrease of baseline HAQ-DI of at least 0.22 at each analysis visit
- Percentage of subjects achieving SF-36v2 of difference  $\geq 5$  at each analysis visit

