5.3.1.3 Acute Phase Reactant (CPR and ESR)

Only CRP is measured during the screening test period. Blood sampling is performed on the scheduled assessment days from baseline to measure CRP and ESR. The measurement of CRP will be performed by the central laboratory (), and the measurement of ESR will be performed by each study center. These results will be used to calculate DAS28, SDAI, and ACR response criteria assessment.

One-hour value of ESR will be measured. The measured ESR and the date of measurement will be entered in the eCRF.

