  - In addition, demographics and other baseline characteristics, and safety results will be provided for all ASP015K treatment groups combined ("ASP015K Total") and for all treatment groups, including placebo, combined ("Total"). Efficacy presentations will not contain combined treatment groups.
  - Chi-square test is continuity corrected in all analysis.
  - Confidence interval for binary outcome is continuity corrected in all analysis.
  - The values below the lower limit of quantitation (BQL) for  $\beta$ -D-glucan, hCG, Troponin, CK-MB will be treated as it is and these variables are not used for descriptive statistics and displayed in the listings. As for  $\beta$ -D-glucan, it is used for shift-from baseline analysis.
  - If anti-CCP antibody (U/mL) is beyond measurement (i.e.  $>500$  U/ml) then Anti-CCP antibody is regarded as 500 U/ml, and categorized in  $>500$  U/ml. Also, if anti-CCP antibody (U/mL) is below measurement (i.e.  $<0.6$  U/ml) then Anti-CCP antibody is regarded as 0.6 U/ml, and categorized in  $<4.5$  U/mL.

- CRP (mg/dL) is below measurement (i.e. <0.01 mg/dL) then CRP is regarded as 0.01 U/ml, and used for the calculation of DAS28-CRP, etc. and categorized in <1.0 mg/dL.
- If Rheumatoid Factor (IU/mL) is below measurement (i.e. <3 IU/mL), then Rheumatoid Factor is regarded as 3 IU/mL and categorized in <- 15 IU/ml.
- Baseline for safety is defined as last non-missing value before the first dose of study drug for all subjects including placebo assigned subjects.
- Baseline for efficacy is defined as value at Day1 before the first dose of study drug for all subjects including placebo assigned subjects.
- Change from baseline to post-baseline will be calculated as: post-baseline value - baseline value. If the baseline value is missing, then that subject is not included in the calculation at any visit.
- Percent change from baseline to post-baseline will be calculated as:  $100 \times (\text{change} / \text{baseline})$ . If the baseline value is 0 or missing, or post-baseline value is missing, then Percent change from baseline to post-baseline is missing.
- If onset date of AE is Unknown, then missing onset date of AE will be imputed as following steps.
  1. If only the day of the month is missing (e.g., 2013-03), then the first day of the month will be used (2013-03-01),
  2. If both day and month are missing (e.g., 2013), then the first day of January will be used (2013-01-01).

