#### **7.4.2 Analysis of Secondary Endpoints**

Refer to Section 10.2 Appendix 2. They include categorical, continuous, and time-to-event variables, with "X" indicating that the variable will be analyzed. As for secondary variables, no multiplicity adjustment will be done. Basically, analysis of secondary endpoints except for mTSS, erosion score, and joint space narrowing score will be performed by Initial Randomization Set and Treatment Sequence Set defined at Section 7.1.

The secondary variables and analyses are as follows:

<Initial Randomization Set>

- Categorical variables at each visit (including Baseline, Weeks 4, 8, 12, 12/ET, Week 28/ET) will be analyzed using Fisher's exact test, as described for the primary efficacy variable, unless otherwise specified in Section 10.2 Appendix 2.
- Raw value and change from baseline variables at each visit (Baseline, Weeks 4, 8, 12, 12/ET, Week 28/ET) will be analyzed using the ANCOVA model with fixed effects for treatment, and baseline value as a covariate.
- Time to the first response analysis will be analyzed similarly as described in 7.4.1.5.
  - ACR50-CRP
  - ACR70-CRP
  - DAS28-CRP <2.6
  - SDAI score <= 3.3
  - CDAI score <= 2.8
  - ACR/EULAR score for remission

As for DAS28-CRP < 2.6, CDAI score <= 2.8, SDAI score <= 3.3, ACR/EULAR score for remission, if the event is occurred at baseline, then that subject is excluded from this analysis.

- Graphical analysis (including Baseline, Weeks 4, 8, 12, 12/ET, Week 28/ET).
  - ACR20/50/70-CRP will be plotted for over time.
  - The mean-standard deviation plot of actual values and changes from baseline will be presented for DAS28-CRP and DAS28-ESR.
  - To visually explore possible relationships between ACR20-CRP and DAS28-CRP, 2-panel line graphs of DAS28-CRP over time will be plotted for ACR20-CRP responders (in 1 panel) and non-responders (in another panel). Similar graphs will be provided for DAS28-ESR.

<Treatment Sequence Set>

- Categorical variables at each visit (including Baseline, Weeks 4, 8, 12, 16, 20, 24, 28, 32, 36, 40, 44, 48, 52, EOT) will be summarized as described in Section 10.2 Appendix 2.
- Raw value and change from baseline variables at each visit (including Baseline, Weeks 4, 8, 12, 16, 20, 24, 28, 32, 36, 40, 44, 48, 52, EOT) will be summarized by descriptive statistics.
- Graphical analysis (including Baseline, Weeks 4, 8, 12, 16, 20, 24, 28, 32, 36, 40, 44, 48, 52, EOT).
  - ACR20/50/70-CRP will be plotted for over time.

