Appendix 1		
6	LOCF DAS28 ACR components	
 
• LOCF all missing DAS28 ACR component value(s) and then calculate the DAS28 score.
 

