#### **7.11.4 Handling of Schedule of Assessments of Efficacy Variables**

For data after the end of study treatment, data obtained within +2 days after the last dose is taken will be included in analysis. Baseline for efficacy is defined as value at Day 1 before the first dose of study drug for all subjects including placebo assigned subjects. For Week

12/ET, or Week 28/ET, the values at closest date to reference date will be used. As for the subjects who switched to receive ASP015K instead of placebo at Week 12, the last observation before first dose of ASP015K at Week 12 will be used for the analysis for visit Week 4, 8, 12, 12/ET. In addition, the subjects who switched to receive ASP015K instead of placebo at Week 28, the last observation before the first dose of ASP015K at Week 28 will be used for the analysis for visit Week 4, 8, 12, 12/ET, 28/ET. For EOT, the closest value to the reference date will be used regardless of the switching from placebo.

(1) TJC (68 joints)/SJC (66 joints), laboratory test (CRP)

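### An ESR of 0 makes DAS28-ESR missing at that assessment, so an observed lowest-possible reading is discarded; a floor value, as already used for CRP, would be better (minor)

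*SAP*

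**What the plan says.** SAP 6.1.2.1 (calculation of DAS28) computes DAS28-ESR as 0.56√TJC28 + 0.28√SJC28 + 0.70 ln(ESR) + 0.014 SGA and adds two separate rules. The general one is "If any component is a missing value, then DAS28-CRP/ESR will be a missing value". The specific one is "If ESR is 0 then DAS28-ESR is missing".

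For CRP, SAP 7.1 does the opposite at the bottom of the scale: "CRP (mg/dL) is below measurement (i.e. <0.01 mg/dL) then CRP is regarded as 0.01 U/ml, and used for the calculation of DAS28-CRP". (The unit printed for the substituted value does not match the rest of that sentence; I read it as 0.01 mg/dL.)

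Three further rules decide what happens next:

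- SAP 7.11.1, Table 4, method 6 carries forward by LOCF "all missing DAS28 ACR component value(s) and then calculate the DAS28 score".
- SAP 7.11.4 adds: "For Week 12/ET, or Week 28/ET, the values at closest date to reference date will be used".
- SAP 7.1 says of change scores: "If the baseline value is missing, then that subject is not included in the calculation at any visit".

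Protocol 5.3.1.3 has each centre measure ESR locally: "One-hour value of ESR will be measured". Neither document gives a lower reporting limit for ESR.

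SAP Appendix 2 compares the DAS28-ESR endpoints with placebo up to Week 28/ET: score below 2.6 (item 3.1), score of 3.2 or less (3.3), EULAR good response (4.1), EULAR good or moderate response (5.1) and change from baseline (13.1.1). SAP 7.4.2 says: "As for secondary variables, no multiplicity adjustment will be done".

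**The concern.** An ESR of 0 is a result, and the most favourable one the test can give. Making the score missing ties missingness to good response: the more a treatment lowers ESR, the more often the rule can apply. At one visit a patient can have a valid DAS28-CRP and no DAS28-ESR, although both markers were measured and both were at their floor.

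The rule also leaves the programming open. Read literally, an observed 0 is not a missing component, so LOCF does not apply and the score stays missing. Read loosely, the 0 is treated as missing and an earlier non-zero ESR, necessarily higher, takes its place. The SAP does not choose between these, and does not say whether a missing DAS28-ESR leaves the denominator or counts as non-response. At stake are the size of the DAS28-ESR remission, low-disease-activity and EULAR differences from placebo, and the mean change.

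**Working it through.** The plan states no figure on this point to reproduce. The check is a reading of the rules followed by a range calculation.

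**1. Which data are lost.** The rule works per assessment. A 0 at Week 12 removes or alters the DAS28-ESR results at Week 12, and possibly Week 12/ET; the same patient's Week 4, Week 8 and later scores stand. The exception is a 0 at baseline, which under SAP 7.1 removes the patient from the change analysis at every visit. Inclusion criterion 6 requires CRP of at least 1.00 mg/dL at screening, so a baseline ESR of 0 should be uncommon (an inference, not a figure in the documents).

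**2. What the score would be with a floor.** With ESR set to 1 mm/h, ln(1) = 0. For illustrative TJC28/SJC28/SGA values:

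| TJC28/SJC28/SGA | ESR 0 set to 1 | earlier ESR of 5 carried forward | earlier ESR of 20 carried forward |
|---|---|---|---|
| 1/1/10 | 0.98 | 2.11 | 3.08 |
| 4/4/30 | 2.10 | 3.23 | 4.20 |
| 9/6/50 | 3.07 | 4.19 | 5.16 |
| 16/9/60 | 3.92 | 5.05 | 6.02 |

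For the second row: 0.56×2 + 0.28×2 + 0 + 0.014×30 = 1.12 + 0.56 + 0.42 = 2.10. Carrying forward an ESR of 5 adds 0.70 ln 5 = 1.13 and moves that patient above both 2.6 and 3.2. The last two rows show that an ESR of 0 does not by itself mean remission.

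**3. Effect on a remission rate.** Inputs: 170 per arm (SAP 4); true remission rate r of 20% to 40% (assumed); share f of the active arm with ESR 0 at the visit, 0.5% to 5% (assumed); all of them remitters and none on placebo (assumed).

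- If they are excluded, bias = (r − f)/(1 − f) − r. For r = 0.30, f = 0.01: 0.29/0.99 − 0.30 = −0.7 points.
- If they are counted as non-responders, bias = −f.

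| f | patients of 170 | excluded, r = 20% to 40% | counted as non-response |
|---|---|---|---|
| 0.5% | 0.9 | −0.4 to −0.3 | −0.5 |
| 1% | 1.7 | −0.8 to −0.6 | −1.0 |
| 2% | 3.4 | −1.6 to −1.2 | −2.0 |
| 5% | 8.5 | −4.2 to −3.2 | −5.0 |

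**4. Effect on the mean.** Excluding patients who score lower than the rest by a gap g shifts the arm mean by f × g. With g of 1 to 2 units (assumed), that is 0.005 to 0.02 at f of 0.5% to 1%, and 0.05 to 0.10 at 5%.

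**5. Effect on a test, as an illustration.** Assume 51/170 (30.0%) on active and 32/170 (18.8%) on placebo; two-sided Fisher p = 0.023. Excluding k remitters from active gives (51 − k)/(170 − k):

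- k = 1: 29.6%, p = 0.023
- k = 3: 28.7%, p = 0.040
- k = 5: 27.9%, p = 0.053

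The crossing of 0.05 depends on the inputs. If only 3 of the 5 are remitters, the rate is 48/165 = 29.1% and p = 0.030. If placebo is 28/170 (16.5%) and all 5 are remitters, p moves from 0.0045 to 0.013.

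**The case against.** The strongest reply is that little depends on this. The endpoints are secondary and unadjusted. DAS28-CRP, which keeps floor values, is analysed in parallel for the same thresholds, EULAR responses and change. Both primary endpoints (ACR20-CRP and mTSS) are outside the rule. Any bias of the kind described would run against the drug, so it could not create a false claim of efficacy. All of this stands, and it is why the point is minor.

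The CRP comparison is also not perfect. The CRP rule covers results reported as below a limit, whereas an ESR of 0 is a recorded reading, and ln(CRP + 1) is defined at 0 anyway. That is fair, but it does not justify discarding a recorded reading when a reported-below-limit one is kept.

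A reader might go further than the documents allow in three ways:

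- That affected patients drop out of every DAS28-ESR analysis. They do not: the loss is per visit, and at Week 12/ET or Week 28/ET an earlier value may stand in.
- That ESR is the only marker not kept at a floor. It is not: SAP 7.1 leaves below-limit β-D-glucan, hCG, troponin and CK-MB out of descriptive statistics, and SAP 7.11.1 sets pharmacodynamic values below the quantification limit to 0.
- That bias is established, or that a significant result would be lost. The frequency of zeros by arm is nowhere in the documents, and the p-values above rest on assumed counts.

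**Conclusion.** The point holds as a minor one. The SAP's rule discards an observed value because of what that value is, differs from its own handling of CRP in the sister score, and leaves LOCF and denominator handling of an ESR of 0 unsettled. If zeros are more common in the arm that lowers ESR more, and those patients have below-average DAS28, that arm's DAS28-ESR result is understated whether the score is dropped or an older ESR is carried forward. Both conditions are plausible; neither is shown in the documents. The size depends wholly on the unknown frequency and, if zeros are rare, is negligible. The upper figures in the tables require up to 5% zeros, all in remission and none on placebo. No confirmatory conclusion is affected.

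**What to change.** Replace the sentence in SAP 6.1.2.1 with: *If ESR is 0 mm/h, it is set to 1 mm/h (ln = 0) for the calculation of DAS28-ESR only; the observed 0 is kept for ESR summaries and ACR-ESR, and is not treated as missing for LOCF.* This keeps the patient in numerator and denominator at the affected visit and removes the choice between readings.

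The cost is one sentence and one line of code, best done before unblinding; SAP section 1 requires later departures to be justified in the study report. The downside is that 1 mm/h is a convention and not a limit given in the documents, and it slightly raises the score. It does not presume remission, as the 9/6/50 example at 3.07 shows.

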### 6.1.2.2 Continuous Variables

Continuous efficacy variables are:

- Raw value and change from baseline in the following assessments:
  - TJC (68 joints)
  - SJC (66 joints)
  - CRP
  - ESR
  - SGAP (VAS) (100 mm VAS)
  - SGA (VAS) (100 mm VAS)
  - PGA (VAS) (100 mm VAS)
  - HAQ-DI (See Section 10.5 Appendix 5: Computation of HAQ-DI Score)
  - DAS28-CRP score
  - DAS28-ESR score
  - SF-36v2®

- SDAI score
- CDAI score
- WPAI score
- mTSS
- Joint Space Narrowing Score
- Erosion Score
- Yearly progression of mTSS

Note: yearly progression will be calculated as follows.

[the final value of mTSS up to Week 52] - [the baseline value of mTSS]

-----x 365.25  
[date of the final value of mTSS up to Week 52] - [date of baseline value of mTSS]

Note: if subject switched from placebo then the final value of that subject is the final value before switching placebo.

